#### 11.1.2 Disease Parameters

Measurable disease. Measurable lesions are defined as those that can be accurately measured in two dimension (longest diameter to be recorded) as  $\geq 20$  mm with conventional techniques (PET/CT, MRI, x-ray) or as  $\geq 10$  mm with spiral CT scan. All tumor measurements will be recorded in millimeters (or decimal fractions of centimeters). Tumor volume will be recorded as the sum of the product of the diameters (SPD) of the largest predominant target lesions.

FDG avidity is based on comparison with background tissues. There is no specific SUV value that is considered a cut-off.

Non-measurable disease (evaluable disease). All other lesions (or sites of disease), including small lesions ( $<10$  mm using spiral CT scan), are considered non-measurable disease. Bone lesions, leptomeningeal disease, ascites, pleural/pericardial effusions, lymphangitis cutis/pulmonitis, inflammatory breast disease, abdominal masses (not followed by CT or MRI), and cystic lesions are all non-measurable.

Target lesions. All measurable lesions up to a maximum of 6 lesions total, representative of all involved organs, should be identified as target lesions and recorded and measured at baseline. Target lesions should be selected on the basis of their SUV avidity (High SUV lesions will be prioritized, even if not the largest lesions) and size (lesions with the largest SPD diameter) and their suitability for accurate repeated measurements (either by imaging techniques or clinically). An SPD for all target lesions will

be calculated and reported as the baseline sum SPD. The baseline sum SPD will be used as reference by which to characterize the objective tumor response based on CT criteria.

**Non-target lesions.** All other lesions (or sites of disease) including any measurable lesions over and above the 6 target lesions should be identified as non-target lesions and should also be recorded at baseline. Measurements of these lesions are not required, but the presence or absence of each should be noted throughout follow-up.

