**ALL SCHEDULED EVENTS +/- 3 DAYS**

## 11. MEASUREMENT OF EFFECT

The primary objective of this study is to evaluate the safety and tolerability of the study drugs. The measurement of toxicity is outlined in Section 7.

Although clinical response is not the primary endpoint of this trial, patients with measurable disease will be assessed by standard criteria. Patients will be re-evaluated at the end of even numbered cycles. Response will be evaluated with physical exam, computerized tomography (CT) and tissue biopsies as defined by the guidelines of the International Harmonization Project Group 2007 Revised Response Criteria. [1] Positron emission tomography / computerized tomography (PET/CT) will be utilized if available (optional). MM patients will be evaluated using criteria described in section 11.2.2

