**Table 10 : Response Criteria for NHL**

Response	Definition	Nodal Masses	Spleen/Liver	Bone Marrow CR
CR	Disappearance of all evidence of disease	a) FDG-avid or PET positive prior to therapy; mass of any size permitted if PET negative (b) Variably FDG-avid or PET negative; regression to normal size on CT	Not palpable, nodules disappeared	Infiltrate cleared on repeat biopsy; if indeterminate by morphology, immunohistochemistry should be negative
PR	Regression of measurable disease and no new sites	50% decrease in SPD of up to 6 largest dominant masses; no increase in size of other nodes	50% decrease in SPD of nodules (for single nodule in	Irrelevant if positive prior to therapy; cell type should be specified

		(a) FDG-avid or PET positive prior to therapy; one or more PET positive at previously involved site (b) Variably FDG-avid or PET negative; regression on CT	greatest transverse diameter); no increase in size of liver or spleen	
SD	Failure to attain CR/PR or PD	(a) FDG-avid or PET positive prior to therapy; PET positive at prior sites of disease and no new sites on CT or PET (b) Variably FDG-avid or PET negative; no change in size of previous lesions on CT		
Relapsed or PD	Any new lesion or increase by 50% of previously involved sites from nadir	Appearance of a new lesion(s) 1.5 cm in any axis, 50% increase in SPD of more than one node, or 50% increase in longest diameter of a previously identified node 1 cm in short axis Lesions PET positive if FDG-avid lymphoma or PET positive prior to therapy	50% increase from nadir in the SPD of any previous lesions	New or recurrent involvement

Abbreviations: CR, complete remission; FDG, [18F]fluorodeoxyglucose; PET, positron emission tomography; CT, computed tomography; PR, partial remission; SPD, sum of the product of the diameters; SD, stable disease; PD, progressive disease.

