### 11.2.3

#### Response Definitions

Complete Response (CR): Disappearance of all non-target lesions by PET/CT

Incomplete Response/Stable Disease (SD): Persistence of one or more non-target lesion(s) and/or maintenance of tumor marker level above the normal limits

Progressive Disease (PD): Appearance of one or more new lesions and/or unequivocal progression of existing non-target lesions

Although a clear progression of “non-target” lesions only is exceptional, the opinion of the treating physician should prevail in such circumstances, and the progression status should be confirmed at a later time by the review panel (or Principal Investigator).

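### Target lesions are prioritised by SUV in Section 11.1.2 but PR in Table 10 rests on the largest masses, so with more than six measurable lesions response can be misclassified in either direction

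*Combined protocol and SAP*

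**What the plan says.** Three parts of Section 11 govern how a partial response is reached.

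- **Section 11.1.2, target lesions.** "All measurable lesions up to a maximum of 6 lesions total, representative of all involved organs, should be identified as target lesions". Selection is by SUV avidity, then size and suitability for repeat measurement, and on avidity the text adds: "High SUV lesions will be prioritized, even if not the largest lesions". The set then becomes the yardstick: "The baseline sum SPD will be used as reference by which to characterize the objective tumor response based on CT criteria".
- **Section 11.1.2, non-target lesions.** Measurable lesions beyond the six fall here. "Measurements of these lesions are not required, but the presence or absence of each should be noted throughout follow-up".
- **Table 10 (Section 11.2.1).** For nodal masses, PR is: "50% decrease in SPD of up to 6 largest dominant masses; no increase in size of other nodes". The PD row includes a 50% increase in the longest diameter of a single previously identified node.
- **Section 11.2.3.** This section is worded for non-target lesions. Incomplete response or stable disease is "Persistence of one or more non-target lesion(s) and/or maintenance of tumor marker level above the normal limits"; progression includes "unequivocal progression of existing non-target lesions". It has no PR category and no rule for combining the non-target result with the target result.

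The opening of Section 11 says that PET/CT "will be utilized if available (optional"). ORR is CR plus PR by best response (Section 11.2.5) and is the phase II primary endpoint (Sections 1.4 and 13.2).

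**The concern.** Up to six measurable lesions, the rules name the same set, because every lesion is a target. Beyond six, they need not. Three consequences follow.

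1. The SPD that decides PR can be computed on the most avid lesions (Section 11.1.2) or the largest masses (Table 10), and the percentage change may differ.
2. SUV exists only if PET/CT was done. Two patients with identical disease can have different target sets because one had an optional scan.
3. Table 10's requirement that other nodes do not increase, and its single-node 50% progression rule, need diameters. Section 11.1.2 asks only whether each non-target lesion is present.

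The primary endpoint depends on this classification. PRs were most of the responders in the romidepsin data cited in Section 2.3.7: 11 of 15 in PTCL and 20 of 24 in CTCL, although the CTCL responses need not have been nodal. The single-node progression rule also bears on dates for DOR and PFS.

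**Working it through.** **1. The plan's own design (Section 13.2).** Inputs: null rate 0.25, alternative 0.50, first stage 9 patients (stop at 2 or fewer responses), total 24 (not pursued at 9 or fewer). With X1 ~ Bin(9, p) and X2 ~ Bin(15, p):

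- Early stopping at p = 0.25: P(X1 ≤ 2) = 0.601 (stated 0.60).
- Expected size: 9 + (1 − 0.601) × 15 = 14.99 (stated 15).
- Power: P(X1 ≥ 3 and X1 + X2 ≥ 10) at p = 0.50 = 0.805 (stated 0.80).
- Type I error: the same probability at p = 0.25 = 0.0485 (stated 0.049; a third-decimal difference, below the 0.05 target).

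The design reproduces, so its boundaries can be used to judge what one patient is worth.

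**2. One patient, two rules.** The sizes are assumed; the documents give none. There are seven measurable nodes: one mass of 100 × 80 mm (8000 mm²) with lower SUV, and six nodes of 30 × 25 mm (750 mm² each) with higher SUV. All exceed both measurability thresholds in Section 11.1.2 (20 mm conventional, 10 mm spiral CT).

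Baseline SPD:
- SUV-first set: 6 × 750 = 4500 mm².
- Six largest: 8000 + 5 × 750 = 11750 mm².

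| Scenario | SUV-first set (11.1.2) | Six largest (Table 10) |
|---|---|---|
| A. Avid nodes each fall 60% to 300 mm²; mass unchanged | 4500 → 1800, −60%: PR threshold met | 11750 → 9500, −19%: not PR |
| B. As A, but mass SPD grows 25% to 10000 mm² | 4500 → 1800, −60%: PR threshold met | 11750 → 11500, −2%: not PR |
| C. Mass shrinks to 50 × 40 mm (2000 mm²); avid nodes unchanged | 4500 → 4500, 0%: not PR | 11750 → 5750, −51%: PR threshold met |

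In B, if the mass grows evenly, each diameter rises by a factor of √1.25 = 1.118, about 12%. That is well short of the 50% single-node rule, but it is an increase in size. Under the SUV-first rule the mass is non-target and nobody is required to measure it.

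A and B push ORR up; C pushes it down.

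**3. What one patient is worth.** 1/24 = 4.2 percentage points. At stage 1, 2/9 stops the trial and 3/9 continues it. At the end, 9/24 is not pursued and 10/24 is.

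**4. Sensitivity of the test.** The misclassification rate m is an assumption; the documents give no value.

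- Upward only, true ORR 0.25, a share m of non-responders scored PR: p = 0.25 + 0.75m.
- Downward only, true ORR 0.50, a share m of responders missed: p = 0.50(1 − m).

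| m | Type I error, upward only | Power, downward only |
|---|---|---|
| 0 | 0.0485 | 0.805 |
| 2% | 0.069 | 0.779 |
| 5% | 0.109 | 0.737 |
| 10% | 0.204 | 0.656 |

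These are one-sided extremes. Errors in both directions would partly offset.

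**The case against.** The strongest reply is that Table 10 is the stated response standard, and a reader who applies it uses the six largest masses and scores scenario A as stable disease. Section 11.1.2 also lists size and asks that targets represent all involved organs, so a bulky mass that is the only lesion in its organ would probably be a target anyway. Its own first paragraph speaks of the largest predominant target lesions. Further, it does not forbid measuring other lesions, and the CT images remain available.

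Much of this stands as a limit on how often the conflict bites. A discordant SUV-based classification needs more than six measurable lesions, a PET/CT, a dominant mass less avid than six others, and a differing response. It does not remove the conflict: Section 11.1.2 expressly allows avidity to outrank size and makes the resulting SPD the CT reference, and nothing says which text prevails.

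Two stronger readings are tempting, and the documents support neither.

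- **That a bulky non-target mass can grow freely without affecting response.** Section 11.2.3 makes unequivocal progression of non-target lesions PD. The gap is narrower: a stable mass, or one growing less than unequivocally. That section's persistence category might be read as blocking PR, but it is worded for non-target lesions and lacks both a PR category and a combination rule, so it leaves the question open.
- **That ORR is biased upward.** Scenario C runs the other way, and the documents do not say whether avid or bulky lesions respond better.

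**Conclusion.** The inconsistency is real and affects the primary endpoint. For patients with more than six measurable lesions, Section 11.1.2 and Table 10 can define different lesion sets, the choice can turn on an optional scan, and two of Table 10's conditions cannot be verified from the records required. Response can be misclassified in either direction: in the assumed example, −60% against −19% one way, and 0% against −51% the other.

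Frequency and net direction are unknown, so no bias in ORR can be quantified; the error-rate table only shows a range. What can be said firmly is that each reclassified patient is worth 4.2 points in a full sample of 24 and can reverse a decision at 2/9 or 9/24. With margins that thin and a correction this cheap, the text should be changed.

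**What to change.** 1. **Section 11.1.2, target lesions.** For every patient, select the up to six largest dominant masses on CT, matching Table 10. Use SUV only to choose between lesions of similar size. The set then no longer turns on whether PET/CT was done, except in such ties.
2. **Section 11.1.2, non-target lesions.** On each response CT already being done, record the longest and short-axis diameters of other nodes that were measurable at baseline. Table 10's condition on other nodes and its single-node progression rule can then be applied.
3. **Section 11.2.3.** State how the non-target result combines with the target result, in particular what overall response follows when targets meet the PR threshold and a non-target lesion persists or grows less than unequivocally.

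The cost is wording in two sections and slightly more reading time, confined to patients with more than six measurable lesions. The number of extra nodes per patient is not capped, so reading time will vary. No extra scan or visit is needed, and treatment is unaffected.

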### 11.1.3

### Methods for Evaluation of Measurable Disease in NHL

All measurements should be taken and recorded in metric notation using a ruler or calipers. All baseline evaluations should be performed as closely as possible to the beginning of treatment and never more than 1 week before the beginning of the treatment.

The same method of assessment and the same technique should be used to characterize each identified and reported lesion at baseline and during follow-up. Imaging-based evaluation is preferred to evaluation by clinical examination when both methods have been used to assess the antitumor effect of a treatment.

**Clinical lesions** Clinical lesions will only be considered measurable when they are superficial (e.g., skin nodules and palpable lymph nodes). In the case of skin lesions, documentation by color photography, including a ruler to estimate the size of the lesion, is recommended.

**CT, PET/CT and MRI** These techniques should be performed with cuts of 10 mm or less in slice thickness contiguously. Spiral CT should be performed using a 5 mm contiguous reconstruction algorithm. This applies to tumors of the chest, abdomen, and pelvis. Head and neck tumors and those of extremities usually require specific protocols.

**Ultrasound (US)** Will not be used for disease assessment

## 11.2 Response Criteria

### 11.2.1 Evaluation of Measurable Disease in NHL

Table 10 outlines the response criteria used to evaluate disease response to therapy.

**Table 10 : Response Criteria for NHL**

Response	Definition	Nodal Masses	Spleen/Liver	Bone Marrow CR
CR	Disappearance of all evidence of disease	a) FDG-avid or PET positive prior to therapy; mass of any size permitted if PET negative (b) Variably FDG-avid or PET negative; regression to normal size on CT	Not palpable, nodules disappeared	Infiltrate cleared on repeat biopsy; if indeterminate by morphology, immunohistochemistry should be negative
PR	Regression of measurable disease and no new sites	50% decrease in SPD of up to 6 largest dominant masses; no increase in size of other nodes	50% decrease in SPD of nodules (for single nodule in	Irrelevant if positive prior to therapy; cell type should be specified

		(a) FDG-avid or PET positive prior to therapy; one or more PET positive at previously involved site (b) Variably FDG-avid or PET negative; regression on CT	greatest transverse diameter); no increase in size of liver or spleen	
SD	Failure to attain CR/PR or PD	(a) FDG-avid or PET positive prior to therapy; PET positive at prior sites of disease and no new sites on CT or PET (b) Variably FDG-avid or PET negative; no change in size of previous lesions on CT		
Relapsed or PD	Any new lesion or increase by 50% of previously involved sites from nadir	Appearance of a new lesion(s) 1.5 cm in any axis, 50% increase in SPD of more than one node, or 50% increase in longest diameter of a previously identified node 1 cm in short axis Lesions PET positive if FDG-avid lymphoma or PET positive prior to therapy	50% increase from nadir in the SPD of any previous lesions	New or recurrent involvement

Abbreviations: CR, complete remission; FDG, [18F]fluorodeoxyglucose; PET, positron emission tomography; CT, computed tomography; PR, partial remission; SPD, sum of the product of the diameters; SD, stable disease; PD, progressive disease.

### 11.2.3

#### Response Definitions

Complete Response (CR): Disappearance of all non-target lesions by PET/CT

Incomplete Response/Stable Disease (SD): Persistence of one or more non-target lesion(s) and/or maintenance of tumor marker level above the normal limits

Progressive Disease (PD): Appearance of one or more new lesions and/or unequivocal progression of existing non-target lesions

Although a clear progression of “non-target” lesions only is exceptional, the opinion of the treating physician should prevail in such circumstances, and the progression status should be confirmed at a later time by the review panel (or Principal Investigator).

### 11.2.4

#### Evaluation of Best Response

The best overall response is the best response recorded from the start of the treatment until disease progression/recurrence (taking as reference for progressive disease the smallest measurements recorded since the treatment started). The patient's best response assignment will depend on the achievement of both measurement and confirmation criteria.

### 11.2.5

#### Overall Response Rate

Overall Response Rate (OR) = CR + PR based on evaluation of best response in each patient.

## **12. DATA REPORTING / REGULATORY REQUIREMENTS**

Adverse event lists, guidelines, and instructions for AE reporting can be found in Section 7.0 (Adverse Events: List and Reporting Requirements).

### **12.1 Data Reporting**

#### **12.1.1 Monitoring**

The Institutional Review Board (IRB) at Columbia University Medical Center will monitor this study.

#### **12.1.2 Responsibility for Data Submission**

The Study Coordinator is responsible for compiling data for all participants and for providing the data to the Principal Investigator for review.

### **12.2 Data Safety Monitoring Board**

The Herbert Irving Comprehensive Cancer Center at Columbia University Medical Center's Data Safety Monitoring Board (DSMB) will oversee conduct of the study, patient safety and all interim analyses as specified in the data analysis plan. Detailed guidelines regarding the structure, function and decision-making mechanisms for the Data Safety Monitoring Board are provided in the DSMB charter.

### **12.3 Investigator Reporting Responsibilities**

The conduct of the study will comply with all FDA safety reporting requirements.

An IND is not needed for this study as both agents are commercially available.

### **12.4 Study auditing**

Investigator responsibilities are set out in the ICH guideline for Good Clinical Practice (GCP) and in the US Code of Federal Regulations.

Investigators must enter study data onto CRFs or other data collection system. The Investigator will permit study-related audits by Celgene or its representatives, IRB/EC review, and regulatory inspection(s) (e.g., FDA, EMEA, TPP), providing direct access to the facilities where the study took place, to source documents, to CRFs, and to all other study documents.

### **12.5 Protocol amendments**

Any amendment to this protocol must be agreed to by the Principal Investigator and reviewed by Celgene. Amendments should only be submitted to IRB/EC after consideration of Celgene review. Written verification of IRB/EC approval will be obtained before any amendment is implemented.

### **12.6 Protocol deviations**

When an emergency occurs that requires a deviation from the protocol for a subject, a deviation will be made only for that subject. A decision will be made as soon as possible to determine whether or not the subject (for whom the deviation from protocol was effected) is to continue in the study. The subject's medical records will completely describe the deviation from the protocol and state the reasons for such deviation. In addition, the Investigator will notify the IRB/EC in writing of such deviation from protocol.

Non-emergency minor deviations from the protocol will be permitted with approval of the Principal Investigator.

## **13. STATISTICAL CONSIDERATIONS**

### **13.1 Study Design/ Primary Endpoints**

#### **Phase I**

This is an open label, single institution Phase I, 3-3 dose-escalation study. The primary objective is to determine the MTD of oral 5-azacitidine in combination with romidepsin. The safety and toxicity of this combination will be evaluated.

All patients who receive any amount of drug will be available for toxicity. Adverse events will be graded using the NCI CTCAE v4.0.

The dose escalation scheme will follow the guideline in Section 5.1.1.

Toxicities will be described by intensity at each dose level

#### **Phase II**

Phase 2 will consist of the combination of oral 5-azacitidine + romidepsin in patients with PTCL. (See figure 2 for study plan flow chart)

#### **Exploratory Cohort**

The Exploratory Cohort will be descriptive in nature.

### **13.2 Sample Size/Accrual Rate**

#### **Phase I**

An estimated 36 patients (max of 45) will be accrued during dose escalation as outlined in Figure 2. Once the MTD is reached 9 further patients will be enrolled at the MTD dose.

The MTD is defined as the level at which  $\leq 1$  out of 3 or  $\leq 2$  out of 6 patients have DLTs at highest dose level below the maximally administered dose.

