#### **Sample Size**

##### Phase I

An estimated 36 patients (max of 45) will be accrued to the initial Phase I study; a minimum of 3 patients will be treated at each of the 6 dose levels (Dose Escalation and de-escalation; Tables 3 & 4). If a DLT is reached early we will treat fewer patients. We will expand the cohort which meets criteria for a DLT to a total of 6.

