#### **2.4.2 Phase I Experience and Determination of MTD**

Twenty-six patients were enrolled in the Phase I study and were evaluable for toxicity. Median age was 51 yrs (23-79) and 58% were male. The median number of prior therapies was 6.5 (range 1-18). Histologies included HL (N=12), DLBCL (N=5), follicular lymphoma (N=3), ATLL (N=2), CTCL (N=2), cutaneous ALCL (N=1), T-ALL (N=1). The entry dose in cohort 1 was azacytidine at 100 mg day 1 to 14 with romidepsin 10 mg/m^2 day 8, 15 every 21 days with no DLT detected. There were 2 DLTs in cohort 2 (azacytidine 200mg day 1 to 14 with romidepsin 10 mg/m^2 day 8, 15 every 21 days) consisting of 1 Grade 3 thrombocytopenia and 1 Grade 3 pleural effusion. In cohort 3, 3 additional patients were evaluated using the every 28 days schedule at the same dose level and no thrombocytopenia and/or other DLTs were observed. Dose escalation was continued until 2 DLT were observed in cohort 7 (azacytidine 300mg day 1 to 21 with romidepsin 14mg/m^2 day 8, 15, 22 every 35 days which resulted in 1 Grade 4 thrombocytopenia and 1 Grade 4 neutropenia. This dose level was declared maximum administered dose (MAD). Patients dosed at the maximum tolerated dose (MTD) of azacytidine 300 mg day 1 to 14 and romidepsin 14 mg/m^2 day 8, 15, 22 every 35 days did not experience any toxicities.

The toxicities reported in >10% of patients included: grade 3/4 toxicities represented by febrile neutropenia (19.2%) and thrombocytopenia (19.2%); grade 2 toxicities represented by back pain (7.7%), fatigue (11.5%), nausea (34.6%), vomiting (19.2%), pain (7.7%) and peripheral sensory neuropathy (7.7%) and grade 1 toxicities including fatigue (38.5%), nausea (23%), diarrhea (19.2%), malaise (19.2%), vomiting (19.2%), anorexia (15.4%), pain (15.4%), constipation (11.5%), cough (11.5%), fever (11.5%), general disorders and administration site complains (11.5%), dyspnea (7.7%), hypokalemia (7.7%), insomnia (7.7%), oral mucositis (7.7%) and pruritus (7.7%).

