#### 5.1.5

#### Maximum Tolerated Dose

The dose-escalation rules and determination of the maximum tolerated dose (MTD) are outlined in Tables 2 and 3. Patients will be enrolled to receive oral 5-azacitidine and romidepsin in sequentially escalating doses until a maximum tolerated dose of the combination has been defined. The maximum tolerated dose of oral 5-azacitidine in combination with romidepsin will be defined as the dose level immediately below the dose level at which greater than or equal to 2 patients out of 6 patients in a cohort experience a dose-limiting toxicity (DLT).

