**Table 3: Dose Escalation & De-Escalation Decision Rules:**

Number of Patients with DLT at a Given Dose Level	Escalation Decision Rule
0 out of 3	Enter 3 patients at the next dose level.
1 out of 3	Enter at least 3 more patients at this dose level. If 0 of these 3 additional patients experience DLT, proceed to the next dose level. If 1 or more of this group experience DLT, then dose escalation is stopped, and this dose is declared the maximally administered dose (MAD), and the dose level below is the MTD.
$\geq 2$	Dose escalation will be stopped. This dose level will be declared the maximally administered dose (highest dose administered).
$\leq 1$ out of 6 at highest dose level below the maximally administered dose	This is generally the recommended phase 2 dose. At least 6 patients must be entered at the recommended phase 2 dose.

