Adverse event (AE) monitoring and reporting is a routine part of every clinical trial. The following list of AEs (Section 7.2) and the characteristics of an observed AE (Section 7.3) will determine whether the event requires expedited (via AdEERS) in addition to routine reporting.

Ongoing monitoring of the clinical safety data in this trial will be performed consistent with procedures outlined in the DSMC charter. This review will pay particular attention to Grade 3 or 4 adverse events, serious adverse events (SAEs), adverse events that lead to discontinuation and adverse events that lead to dose reduction. Should the incidence of any particular adverse event, or combination of events, rise to a level of clinical concern the DSMC will be notified for possible review of the emergent adverse events.

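### Section 13.2 defines the MTD more loosely than Table 3 and 5.1.5 and still plans 9 MTD patients that Phase I cannot have included; the protocol sets no numerical study-level toxicity limit for Phase II.

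*Combined protocol and SAP*

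**What the plan says.** **MTD definition.** Section 13.2 (Phase I) defines the MTD as the level where at most 1 of 3, or at most 2 of 6, "patients have DLTs at highest dose level below the maximally administered dose". Section 5.1.5 defines it as the level immediately below one at which "greater than or equal to 2 patients out of 6 patients in a cohort experience a dose-limiting toxicity (DLT"). Table 3 stops escalation when a first DLT among 3 is followed by one or more among the next 3. It wants at most 1 of 6 at the recommended phase 2 dose and adds: "At least 6 patients must be entered at the recommended phase 2 dose".

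**Numbers.** Section 13.2 plans an estimated 36 Phase I patients (maximum 45) and states: "Once the MTD is reached 9 further patients will be enrolled at the MTD dose". The synopsis says that "a minimum of 3 patients will be treated at each of the 6 dose levels". Section 2.4.2 then reports the phase as done: "Twenty-six patients were enrolled in the Phase I study and were evaluable for toxicity". Escalation ran to cohort 7, where two DLTs made that level the maximum administered dose. Patients at the MTD are said to have had no toxicities, without a count.

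**Safety limits after Phase I.** Phase II takes 24 patients and the germinal-centre (GC) cohort 10, all at this dose. Section 12.2 says the DSMB "will oversee conduct of the study, patient safety and all interim analyses as specified in the data analysis plan" and leaves its decision mechanisms to a charter. Section 7.1 says: "Should the incidence of any particular adverse event, or combination of events, rise to a level of clinical concern the DSMC will be notified". Sections 5.1.6 and 6.1 and the romidepsin dose-modification table act on individual patients. The numerical study-level rules in 13.2 (2 of 9, then 9 of 24) concern response.

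**The concern.** Two DLTs in six is acceptable in one section and too toxic in two others, so the protocol has no single standard for judging DLTs at this dose. The planned expansion would have given the dose a firmer safety base, but it does not appear in the reported Phase I. A report of no toxicities also means much less from 3 patients than from 8. The same dose then goes to 24 + 10 = 34 patients, and the protocol's own study-level trigger for toxicity carries no number.

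**Working it through.** **1. The plan's Phase I total.** 6 levels × 6 patients = 36, and 36 + 9 = 45. This reproduces the stated estimate and maximum. The documents do not give this derivation, but it fits, and it places the 9 patients inside Phase I.

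**2. Can the 26 include the 9?** Section 5.1.6 labels the next three levels down as Cohorts 5, 4 and 3, so the MTD was cohort 6 of 7.
- With at least 3 in each of the other six cohorts, the MTD had at most 26 − 6×3 = 8.
- If cohorts 2 and 7, which had two DLTs each, stopped at 2 patients, the ceiling is 26 − (4×3 + 2×2) = 10.
- An MTD cohort of 3 plus 9 further patients needs 12. That would leave 26 − 12 = 14 for the other six cohorts, which need 18, or 16 in the looser case.

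Neither reading leaves room for the 9.

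**3. How many were at the MTD?** With at least 3 in all seven cohorts, the number is 8 − e, where e = 0 to 5 is the count of extra patients in the other six. That gives 3 to 8. Table 3's minimum of 6 is met if e ≤ 2 and missed otherwise.

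**4. What zero DLTs would show.** The one-sided 95% upper bound is 1 − 0.05^(1/n).

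| n with 0 DLTs | Upper bound on DLT risk |
|---|---|
| 3 | 63% |
| 6 | 39% |
| 8 | 31% |
| 12 (3 + 9) | 22% |

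**5. The two MTD limits.** Exact binomial probability that a dose with true DLT risk p passes in 6 patients:

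| p | At most 2 of 6 (13.2) | At most 1 of 6 (Table 3) |
|---|---|---|
| 20% | 90% | 66% |
| 33% | 69% | 36% |
| 50% | 34% | 11% |

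At 33%, Table 3's sequential rule (0 of 3, or 1 of 3 then 0 of 3) passes the dose with probability 43%.

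**6. A possible Phase II limit.** The documents state no target DLT rate, so the risks below are assumed. Exact binomial, first 9 patients:

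| p | 3 or more of 9 | 4 or more of 9 |
|---|---|---|
| 20% | 26% | 9% |
| 25% | 40% | 17% |
| 33% | 61% | 34% |
| 40% | 77% | 52% |
| 50% | 91% | 75% |

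**7. Lag.** The DLT window is 35 + 7 = 42 days, and about 22 + 30 = 52 days for a patient who stops after cycle 1 (Section 5.2). At 4 Phase II patients a month, 4 × 42/30.4 = 5.5 enter during a 42-day window. Adding 1 to 2 GC patients a month gives 5 × 42/30.4 = 6.9 to 6 × 42/30.4 = 8.3. A simulation with evenly spaced entry at 4 a month and DLT timing assumed uniform over 42 days puts about 8 to 9 Phase II patients already enrolled when a hold occurs at 33% to 50% risk (8.8 on average at 33%).

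**The case against.** The strongest reply is that Phase I is finished and the dose is fixed. Table 3 and 5.1.5 agree with each other, only one sentence in 13.2 is out of line, and no toxicities are reported at the MTD. This largely stands: the conflict probably changed nothing about the dose. A reader might infer that the dose was picked under the looser rule, or that cohort 7 would have qualified under 13.2 had it held 6 patients. The documents do not support either, since the size of cohort 7 is not given and the level was declared too high.

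Second, the range of 3 to 8 is inferred. The synopsis minimum refers to six dose levels, while seven cohorts were run. The synopsis also says a cohort meeting DLT criteria is expanded to 6; applied to cohorts 2 and 7, that leaves 26 − (4×3 + 2×6) = 2 at the MTD, so not every stated size rule can have been followed. Text directly after Section 2.4.2 and the Phase I flow chart were not available and may give the count. A reader might conclude that Table 3's minimum of 6 was breached. The available text only fails to show that it was met.

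Third, the DSMB and DSMC charters were not available. It would be wrong to infer that the trial has no toxicity limit; only the protocol is silent. Oversight and patient-level rules do exist.

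Fourth, a limit of 3 in 9 is a choice, and it counts only 9 of the 34 patients. Both are true. It is also tempting to credit a running count with catching the third DLT among the first 6 patients, with probability 31%, 46% and 66% at 33%, 40% and 50% risk. Those figures say which patients have the DLTs, not when they are known. With the lag in step 7, the third DLT is known with 6 or fewer enrolled in only about 10%, 16% and 26% of trials.

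**Conclusion.** The point holds in limited form.

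- **Firm:** the MTD limit in 13.2 contradicts Table 3 and 5.1.5, and it roughly doubles the chance of accepting a dose with 33% DLT risk (69% against 36%).
- **Firm on either cohort-size reading examined:** the 9 further patients are not among the 26.
- **Conditional:** the MTD cohort held 3 to 8 patients if every cohort had at least 3, and up to 10 if cohorts 2 and 7 stopped at 2.
- **Limited to the protocol text:** there is no numerical study-level toxicity limit for Phase II or the GC cohort.

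The documents do not show that the dose is wrong, that Table 3 was violated, or that safety oversight is absent. Whether the expansion was dropped, is pending or was folded into Phase II is not stated.

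**What to change.** 1. In 13.2, change the MTD definition to at most 1 of 6, matching Table 3 and 5.1.5.
2. Delete the 9-patient sentence, or say what became of that step.
3. State in 2.4.2 how many patients were treated at the MTD. If fewer than 6, apply Table 3 (at most 1 of 6) to the first Phase II patients until 6 are reached.
4. Unless the DSMB charter already sets a limit, add to 13.2 a hold on Phase II and GC accrual for DSMB review, not termination, at the third cycle-1 DLT (Section 5.2) among the first 9 Phase II patients. Three is a suggested value. Four would cut false holds at 20% risk from 26% to 9%, but would detect a 33% risk only 34% of the time instead of 61%.

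**Cost.** Items 1 and 2 and the count in item 3 are text edits. The hold needs no extra patients or visits, because cycle-1 safety checks on Days 1, 8, 15 and 22 are already scheduled. The price is a possible pause in accrual, including a false hold in about 1 of 4 trials at 20% risk. Because of the lag, the gain is mainly to patients after the first 9. DLTs in later Phase II patients and in the GC cohort would not count toward this limit.
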